10.3 POPULATIONS FOR ANALYSES

10.3.1 Evaluable for toxicity

All participants will be evaluable for toxicity from the time of their first treatment with BMS-986253.

10.3.2 Evaluable for objective response

Only those participants who have measurable disease present at baseline, have received at least one cycle of therapy with study drug, and have had their disease re-evaluated will be considered evaluable for response. These participants will have their response classified according to the definitions stated below. (Note: Participants who exhibit objective disease progression prior to the end of cycle 1 will also be considered evaluable.)

10.4 STATISTICAL ANALYSES

10.4.1 General Approach

- Participants in phase I will be evaluated for safety, reporting the toxicities noted per dose level.
- Participants in phase II will have their response rate reported along with a confidence interval.

10.4.2 Analysis of the Primary Endpoints

- Participants enrolled in phase I will have the grades and types of toxicity reported at each dose level separately by cohort. The overall estimate of the fraction of participants who have a DLT at the OBD will be reported by cohort.
- Participants evaluated in phase II will have the fraction with clinical responses reported separately by cohort, with a separate 95% confidence interval for each cohort.

10.4.3 Analysis of the Secondary Endpoint(s)

- The secondary objectives for phase I are to describe pharmacokinetic properties of BMS-986253 in MDS participants and to evaluate safety and tolerability of BMS-986253 in MDS participants. The AUC, half-life, and Css of BMS-986253 will be evaluated in participants, separately by dose level and cohort using descriptive statistics.
- The secondary objectives for phase II are:
 - (a) to evaluate the safety and tolerability of the agent as measured by the grades and types of toxicity noted for the agent at each dose level, separately by cohort; and,
 - (b) to evaluate efficacy, as measured by clinical outcomes, including OIR (CR + PR + HI + marrow CR + SD), cytogenetic response rate, time to best response, disease free survival (DFS; definition: time to relapse for participants who achieve CR), progression free survival (PFS; definition: disease progression or death from MDS), leukemia free survival (LFS; definition: progression to AML or death from any cause), and overall survival (OS; definition: death from any cause).
 - OIR and cytogenetic response rate will each be reported as a fraction, separately by cohort, along with a 95% confidence interval. Time to best response, DFS,

PFS, LFS, and OS will be evaluated separately for each phase II cohort using the Kaplan-Meier method. In each case, the median time to event will be reported along with a 95% confidence interval for the median.

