1.1.2.2 Phase II

- To evaluate safety and tolerability of BMS-986253 with or without DNMTi in MDS participants, as well as clinical outcomes including overall improvement rate (OIR), transfusion-independence (TI), cytogenetic response rate, time to best response (CR, PR, marrow CR + HI, HI), disease free survival (DFS: definition: time to relapse for participants who achieve CR), progression-free survival (PFS; definition: disease progression or death from MDS), leukemia-free survival (LFS; definition: progression to AML or death from any cause), and overall survival (OS: definition: death from any cause).

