2 ELIGIBILITY ASSESSMENT AND ENROLLMENT

2.1 ELIGIBILITY CRITERIA

2.1.1 Inclusion Criteria

1. Participants must have histologically or cytologically confirmed MDS according to 2016 WHO criteria[1]
 - a. And:
2. have HR-MDS (R-IPSS ≥ 3.5) and received a minimum of 2 and maximum of 8 prior cycles for phase I and 4 for phase II of DNMTi therapy, or
3. have LR-MDS (R-IPSS <3.5),
 - a. and, at least one cytopenia:
 - i. granulocytes $< 1.0 \times 10^9/L$ and/or
 - ii. hemoglobin $< 110 \text{ g/L}$ with signs/symptoms of symptomatic anemia or transfusion-dependency
 - iii. platelets $< 100 \times 10^9/L$

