6.3.1 Response Criteria

The table below shows the 2006 International Working Group response criteria for altering the natural history of MDS,[\[115\]](#) with modified definitions for HI-E, HI-P, and HI-N in the suggested 2018 International Working Group response criteria.[\[85\]](#)

Category	Response criteria (responses must last at least 4 weeks)
Complete remission	
 • Bone marrow: $\leq 5\%$ myeloblasts with normal maturation of all cell lines* • Persistent dysplasia will be noted* • Peripheral blood† 
 • Hgb ≥ 11 g/dL • Platelets $\geq 100 \times 10^9/L$ • Neutrophils $\geq 1.0 \times 10^9/L$ • Blasts 0%
Partial remission	All CR criteria if abnormal before treatment except: 
 • Bone marrow blasts decreased by $\geq 50\%$ over pretreatment but still $> 5\%$ • Cellularity and morphology not relevant
Marrow CR	
 • Bone marrow: $\leq 5\%$ myeloblasts and decrease by $\geq 50\%$ over pretreatment • Peripheral blood: if HI responses, they will be noted in addition to marrow CR

Stable disease	Failure to achieve at least PR, but no evidence of progression for >8 wks
Failure	Death during treatment or disease progression characterized by worsening of cytopenias, increase in percentage of bone marrow blasts, or progression to more advanced MDS FAB subtype than pre-treatment
Relapse after CR or PR	At least 1 of the following: 
 Return to pre-treatment bone marrow blast percentage Decrement of $\geq 50\%$ from maximum remission/response levels in granulocytes or platelets Reduction in Hgb concentration by ≥ 1.5 g/dL or transfusion dependence
Cytogenetic response	Complete 
 Disappearance of the chromosomal abnormality without appearance of new ones Partial 
 At least 50% reduction of the chromosomal abnormality
Disease progression	For participants with: 
 Less than 5% blasts: $\geq 50\%$ increase in blasts to $>5\%$ blasts 5%-10% blasts: $\geq 50\%$ increase to 10% blasts 10%-20% blasts: $\geq 50\%$ increase to $>20\%$ blasts 20%-30% blasts: $\geq 50\%$ increase to $>30\%$ blasts Any of the following: 
 At least 50% decrement from maximum remission/response in granulocytes or platelets Reduction in Hgb by ≥ 2 g/dL Transfusion dependence

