Phase II: To evaluate safety and secondary clinical outcomes of BMS-986253 in MDS participants by cohort.	-Safety, as measured by: Incidence of AEs, SAEs; and AEs leading to discontinuation, death, and laboratory abnormalities, assessed from first cycle until time of disease relapse, disease progression, or death, whichever occurs first, assessed every 3-6 months - Clinical outcomes including: overall improvement rate (OIR), cytogenetic response rate, time to best response (CR, PR, marrow CR, or HI), disease free survival (DFS; definition: time to relapse for participants who achieve CR), progression free survival (PFS; definition: disease progression or death from MDS), leukemia free survival (LFS; definition: progression to AML or death from any cause), and overall survival (OS; definition:	Confirm safety and evaluate efficacy through long-term clinical outcomes

OBJECTIVES	ENDPOINTS	JUSTIFICATION FOR ENDPOINTS
	death from any cause); assessed every 3-6 months	
Exploratory		
To evaluate changes in serum cytokine levels pre- and post-treatment with BMS-986253.	Each of these will be evaluated using descriptive methods and reported as exploratory results. If any statistical tests are performed in these analyses, the results will be presented without adjustment for multiple comparisons but reported in the context of the number of tests performed. See section 5 for collection timepoints.	Evaluate mechanistic and immunologic effects of the study drug
To evaluate the cell composition in the peripheral blood and bone marrow microenvironment before and after treatment with BMS-986253.		
To evaluate changes in the transcriptome and proteome in response to treatment with BMS-986253.		
To determine the degree of bone marrow myeloid-derived suppressor cell (MDSC) infiltration.		
To describe changes in genetic clonal diversity during treatment with BMS-986253 in combination with DNMTi.		
To assess cell-autonomous effects on the MDS clone by measuring biomarkers in the Akt pathway (i.e. pS743) in MDS blasts.		
To evaluate cell-autonomous and microenvironment dependent activity of BMS-986253 using ex vivo culture of participant-derived		

OBJECTIVES	ENDPOINTS	JUSTIFICATION FOR ENDPOINTS
hematopoietic stem and progenitor cells.		
To assess quality of life improvement by participant reported outcomes using the EORTC QLQC30 score.		

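### The overall improvement rate counts stable disease, so in lower-risk MDS it mainly measures 8-week non-progression, and no planned rate isolates hematologic improvement

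*Combined protocol and SAP*

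**What the plan says.** All references are to the combined protocol and SAP.

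- **Definition.** Section 10.4.3 gives the components: "OIR (CR + PR + HI + marrow CR + SD". It is the only place that does. Section 1.1.2.2 ("overall improvement rate (OIR), transfusion-independence (TI), cytogenetic response rate") and section 10.1 ("overall improvement rate (OIR), cytogenetic response rate, time to best response") name the endpoint without saying what counts.
- **Stable disease.** Section 6.3.1, repeated in Appendix D, defines it as "Failure to achieve at least PR, but no evidence of progression for >8 wks".
- **Analysis.** Section 10.4.3 states: "OIR and cytogenetic response rate will each be reported as a fraction, separately by cohort, along with a 95% confidence interval". There is no null value, target or comparator.
- **Primary response.** Section 10.2 counts CR, PR and marrow CR with HI in both cohorts. It counts neither SD nor HI alone.
- **Lower-risk hypothesis.** Section 1.2.5 expects monotherapy to improve cytopenia in lower-risk participants.

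**The concern.** The name promises improvement, but one component requires none. A participant whose counts, marrow and transfusion need are unchanged for a little over 8 weeks is scored the same as one in complete remission.

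The HI component also loses most of its effect. A participant with HI who is short of PR and has not progressed for more than 8 weeks already meets the SD definition. Erythroid HI itself needs at least 8 weeks, so erythroid responders are almost all counted through SD anyway. Platelet and neutrophil HI carry no separate 8-week requirement in the table, so the overlap there is likely but not built in.

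This matters most in the lower-risk cohort, where HI is the benefit that the trial looks for. The primary rate in section 10.2 gives HI alone no credit. Section 10.4.3 analyses only two secondary efficacy rates as fractions with an interval: OIR and cytogenetic response. OIR is therefore the only planned rate that could show an HI effect, and its definition largely removes that ability. A published single-arm improvement rate near 90%, with no reference value, would invite reading as drug effect.

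**Working it through.** **1. The plan's own figures.** The documents state no expected OIR. The nearest stated figure is the lower-risk Simon design, which sets the cohort size for OIR (12, then 25; p0 = 0.20, p1 = 0.40). Early termination under the null is P(X ≤ 2 | n = 12, p = 0.20) = 0.0687 + 0.2062 + 0.2835 = 0.558, against a stated 55.8%. The full two-stage rule gives alpha 0.099 and power 0.815. The higher-risk design also reproduces: early termination 72.2%, alpha 0.0997, power 0.804. Neither design uses OIR.

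**2. What an inert drug would score.** If nobody improves, OIR equals q, the probability of no progression for 8 weeks. The documents' prognosis figures, read as exponential with 52.18 weeks per year, give upper bounds only:

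- Alive at 8 weeks, lower-risk median survival 5.9 years (section 1.2.1): 0.5^(8/(5.9 × 52.18)) = 98.2%.
- Free of AML at 8 weeks (Appendix C): Low group, 25% by 10.8 years, 0.75^(8/(10.8 × 52.18)) = 99.6%. Intermediate group, 25% by 3.2 years, 98.6%.

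Protocol progression is broader than death or AML. It includes "At least 50% decrement from maximum remission/response in granulocytes or platelets", a hemoglobin fall of 2 g/dL or more, and transfusion dependence. Lower-risk eligibility admits low hemoglobin "with signs/symptoms of symptomatic anemia or transfusion-dependency". So q must be assumed. With q = 0.5^(8/median in weeks):

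| Assumed median time to progression | q | Expected of 25 counted as improved |
|---|---|---|
| 3 months (pessimistic) | 65% | 16.3 |
| 6 months | 81% | 20.2 |
| 12 months | 90% | 22.5 |
| 24 months | 95% | 23.7 |
| 36 months | 97% | 24.1 |

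**3. How far a real effect moves OIR.** Let r be the true improvement rate (CR, PR, marrow CR or HI) and q now the 8-week non-progression probability among non-improvers. Then OIR = r + (1 − r)q, and two drugs with rates r1 and r2 differ by (r2 − r1)(1 − q). The lower-risk p0 and p1 are borrowed as illustrative values of r:

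| q | OIR at r = 20% | OIR at r = 40% | Difference with SD | Difference without SD |
|---|---|---|---|---|
| 0.80 | 84% | 88% | 4 points | 20 points |
| 0.90 | 92% | 94% | 2 points | 20 points |
| 0.95 | 96% | 97% | 1 point | 20 points |
| 0.98 | 98.4% | 98.8% | 0.4 points | 20 points |

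At the pessimistic q = 0.65 the two rates are 72% and 79%, a difference of 7 points.

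**4. Against the precision available.** An observed 23 of 25 (92%) has a Clopper-Pearson 95% interval of 74% to 99%. Differences of 1 to 4 points are far inside it.

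**The case against.** The strongest defence is that the formula is printed openly and that stability has value. Section 12.3.2 names stable disease as a potential benefit, and section 6.3 groups SD with PR and HI when it describes who may receive further therapy. A composite that includes SD is a legitimate quantity. That stands, but it supports reporting disease control under that name, not calling it improvement.

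The consequences are also limited. OIR has no threshold, and section 10.2 calls overall survival the most important secondary endpoint. That stands too.

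Three stronger readings are tempting, and the documents do not support them:

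- **That OIR would approach 100% whatever the drug does.** The survival and AML figures give ceilings of about 98% to 99%, but protocol progression is wider than either, and no lower-risk progression rate is given. With fast progression the figure could be as low as 65%.
- **That sections 10.1 and 10.4.3 give conflicting definitions of OIR.** The list in section 10.1, "time to best response (CR, PR, marrow CR, or HI", belongs to a different endpoint. It shows that SD is not treated as a best response there, but it does not define OIR.
- **That an HI signal could not be seen at all.** HI enters time to best response, which is analysed by Kaplan-Meier. Appendix F records HI, marrow CR with and without HI, and SD as separate categories, so the count can be recovered. Transfusion independence is a named objective in section 1.1.2.2, although sections 10.1 and 10.4.3 do not carry it forward. What is missing is a prespecified rate.

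**Conclusion.** The point holds as a defect in a secondary endpoint. That SD counts as improvement, and that the primary rate excludes HI alone, follow directly from the text and need no assumption.

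The size does rest on assumptions. An inert drug in the lower-risk cohort would score about 81% to 97% if time to progression is exponential with a median of 6 to 36 months. Improvement rates of 20% and 40% would be compressed from 20 points apart to about 1 to 4 points if 95% to 80% of non-improvers pass 8 weeks without progression. Outside those ranges the figures change, but some compression remains for any q above zero.

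A reader might infer that the trial's go/no-go decision is compromised. It is not: the primary response excludes SD, so the Simon boundaries, alpha, power and sample size are untouched. The change should be made, but the trial's main conclusion does not depend on it.

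**What to change.** - In section 10.4.3, define OIR as CR + PR + marrow CR + HI, reported by cohort with its 95% confidence interval.
- Report SD on its own line, or report OIR + SD as a separate quantity named disease control.
- Put the same definition in sections 1.1.2.2 and 10.1.

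Appendix F already captures each category at every response assessment and as best overall response, so no new data, visits or participants are needed. The cost is a wording change in three sections and a less favourable figure.

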1.2.5 Rationale for Myeloid Malignancy Program Investigation

In general, long term treatment outcomes for MDS participants are dismal. It is estimated that of every 100 MDS participants, four will be long-time survivors, with the rest of succumbing to either MDS- or treatment-related complications (67) or MDS-unrelated complications (29).^[3] There has been no progress in populations based studies in survival of MDS participants during last 2 decades.^[77] Novel approaches are needed which do not rely exclusively on cytotoxic therapy and/or intervene earlier in the course of the disease. Current clinical trials for participants with MDS enroll less than 5% of MDS participants.^[76] With better understanding of complex MDS pathophysiology, trials using combination treatments are emerging, especially for those ineligible for the HSCT, therefore representing an unmet need.^[11]

Since immune disturbance in MDS is common pathologic finding,^[101] and MDSCs have been found to induce myelodysplasia,^[60] with evidence of VEGF-independent neoangiogenesis and overexpression of EMT transcription factors as important processes in the evolution of MDS,^[53] there is a reasonable evidence that by blocking IL-8-mediated processes with IL-8 neutralization, a positive, disease-modifying therapeutic effect could be achieved. Preclinical *in vitro* work has also shown that blockade of the IL-8 receptor, CXCR2, led to significant reduction in the proliferation of several leukemic cell lines and primary AML/MDS cells. ^[37]

In the preclinical experiments done in Laboratory of Receptor Biology and Gene Expression (NCI/CCR), a heterozygous U2AF1 mutation was found to lead to widespread changes in translation such that mutant cells showed a ‘non-oncogene addiction’ to the ribosome biogenesis machinery.^[69] These data indicate an unanticipated functional connection between a splicing factor mutation and the ribosome biogenesis machinery. The preceding observations necessitate clinical correlates which specifically interrogate post-transcriptional regulation in MDS. Although there has been exhaustive DNA and RNA sequencing in MDS, there has been little if any quantitative measurements of translational regulation and this trial will allow a novel insight in the pathophysiology if MDS in synergy with the ongoing basic laboratory NCI/CCR research.

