 2. NIH developed psychosocial assessment scale – see questionnaire

Data collection during study/treatment

- Cycle number & day of treatment
- Study Drug Administration
- Disease response at assessment timepoints: CR (complete response), PR (partial response), HI (hematologic improvement), mCR with HI (marrow CR with hematologic improvement), mCR without HI (marrow CR without hematologic improvement), SD (stable disease), PD (disease progression)
- Best overall response to study treatment: CR (complete response), PR (partial response), HI (hematologic improvement), mCR with HI (marrow CR with hematologic improvement), mCR without HI (marrow CR without hematologic improvement), SD (stable disease), PD (disease progression)
- Bone marrow percent blasts
- RBC transfusion dependence (transfusion dependent or transfusion independent)
- Platelet transfusion dependence (transfusion dependent or transfusion independent)
- # of transfusions per month (RBCs units and instances of platelets transfusions)
- Adverse events
- Patient Reported Outcome Questionnaires: (per section [3.5.3](#))
 - EORTC QLQC30 score (patient reported) – see questionnaire
 - NIH developed psychosocial assessment scale – see questionnaire

Data collection at post-therapy follow-up visits

- Alive (yes/no)
- Adverse events
- Progression of MDS (if yes, to what and when)
- Diagnosed with sAML (yes/no)
 - If diagnosed with sAML, date of sAML diagnosis (month, year)
 - subsequent MDS/AML specific treatments including BMT until off study if information available.

Data collection at time of death

- Date of death
- Disease status at time of death: CR or not CR
- Cause of death: disease progression/relapse vs non-relapse mortality (definition of non-relapse mortality: subject in clinical remission at time of death)
- If non-relapse mortality, primary cause of death (e.g., infection, organ failure, other – per CTCAE)

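### PFS counts only deaths from MDS and DFS counts no deaths, yet both go to Kaplan-Meier, so the curves estimate neither all-cause PFS/DFS nor the probability of avoiding the defined event

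*Combined protocol and SAP*

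**What the plan says.** Section 10.4.3 (Analysis of the Secondary Endpoint(s)) gives the event for "progression free survival (PFS; definition: disease progression or death from MDS" and the event for "disease free survival (DFS; definition: time to relapse for participants who achieve CR". The estimator sentence in the same section begins with "Time to best response, DFS" and continues "PFS, LFS, and OS will be evaluated separately for each phase II cohort using the Kaplan-Meier method", with a median and 95% confidence interval in each case. LFS and OS, by contrast, count death from any cause.

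Sections 1.1.2.2, 3.5.2, 6.3.1, 10.1 and Appendix D give the same PFS and DFS definitions. None of them gives a censoring rule, a competing-risks method, a definition of death from MDS, or a process for adjudicating cause of death.

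Appendix F records at death: "Cause of death: disease progression/relapse vs non-relapse mortality (definition of non-relapse mortality: subject in clinical remission at time of death". A primary cause is then asked for only if the death is non-relapse mortality.

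On how common other deaths are, section 1.2.5 divides 100 patients into four long-term survivors, 67 dying of MDS- or treatment-related complications, and the rest of "MDS-unrelated complications (29". Section 1.2.1 puts the unrelated share at about one third.

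**The concern.** Kaplan-Meier has only two states for a participant: event or censored. Under these definitions a non-MDS death before progression (PFS), or any death before relapse (DFS), is not an event, so it must be censored. Censoring treats that participant as still able to progress or relapse later, which is untrue.

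The result has no clear meaning. It is not the proportion alive without progression, because some of those who died are carried forward as if alive. Nor is it the proportion who avoid progression and MDS death, because people who died of something else have in fact avoided that event. It describes a hypothetical setting in which other deaths do not occur, and only if those deaths are independent of progression. The plan does not name that as its target.

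At stake are the medians and intervals for two secondary endpoints in each phase II cohort. PFS also depends on attributing cause of death in an open-label, single-arm trial, using a form that is not built for it.

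**Working it through.** The documents give no planned median, event count or power for PFS or DFS, so there is no figure of the plan to reproduce.

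**Inputs from the protocol**
- Share of deaths unrelated to MDS, f: 0.29 (section 1.2.5, 29 of 100 patients; as a share of deaths, 29/(67+29) = 0.30) to 1/3 (section 1.2.1).
- Median OS: 1.5 years in higher-risk and 5.9 years in lower-risk MDS (section 1.2.1).
- Phase II size: 32 and 25 evaluable participants (section 10.2).

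**Assumptions**
- Constant hazards.
- Non-MDS death hazard c = f × ln 2 / (median OS).
- Hazard of progression or MDS death l = ln 2 / m, where m is the median that Kaplan-Meier would report. No document gives m, so it is varied: 0.75 to 2.25 years (higher risk) and 2 to 8.85 years (lower risk).

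**Three quantities at time t**
- Kaplan-Meier with other deaths censored: exp(−l t)
- All-cause PFS: exp(−(l + c) t)
- Probability of no progression or MDS death (one minus cumulative incidence): 1 − [l/(l + c)] × [1 − exp(−(l + c) t)]

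The Kaplan-Meier median divided by the all-cause median is 1 + c/l = 1 + f m / (median OS).

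**Higher risk, f = 1/3, m = 1.0 year, t = 2 years**
- c = 0.6931/1.5/3 = 0.154; l = 0.693; l + c = 0.847
- Kaplan-Meier: exp(−1.386) = 25.0%
- All-cause: exp(−1.694) = 18.4%, which is 6.6 points lower
- One minus cumulative incidence: 1 − 0.818 × 0.816 = 33.2%
- All-cause median 0.693/0.847 = 0.82 year; ratio 1.22

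**Lower risk, f = 1/3, m = 3.0 years, t = 5 years**
- c = 0.6931/5.9/3 = 0.039; l = 0.231; l + c = 0.270
- Kaplan-Meier: exp(−1.155) = 31.5%
- All-cause: exp(−1.351) = 25.9%, which is 5.6 points lower
- One minus cumulative incidence: 1 − 0.855 × 0.741 = 36.6%
- All-cause median 0.693/0.270 = 2.57 years; ratio 1.17

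Simulation at the planned sizes agrees: 24.8% against 18.2% with 32 participants, and 31.5% against 26.0% with 25.

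**Range of the median ratio**
- Lowest: lower risk, f = 0.29, m = 2: 1 + 0.29 × 2/5.9 = 1.10
- Highest: higher risk, f = 1/3, m = 2.25: 1 + (1/3) × 2.25/1.5 = 1.50. Lower risk with m = 8.85 gives the same. At this end the all-cause median equals median OS, meaning that nobody progresses before death, so 1.50 is an outer bound.

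**DFS.** The same algebra applies, but the documents give no relapse or death rate after CR, so no size can be computed.

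**Case report form.** Consider a participant with stable disease who dies of an unrelated cause. Appendix F offers progression/relapse, which is not what happened, or non-relapse mortality, which requires clinical remission. Neither fits, and no primary cause is requested. Whether this death is a PFS event is left open.

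**The case against.** The definitions are the same throughout and are presented in section 6.3.1 as the cited International Working Group criteria, so the plan does not contradict itself here. The endpoints are secondary and descriptive, with no test or decision attached. OS, which section 10.2 calls the most important secondary endpoint, and LFS count all deaths. Event-free survival with any-cause death is defined in section 6.3.1 and listed for follow-up in sections 3.1 and 3.4. All of this stands and limits the weight of the point. It does not make Kaplan-Meier suitable for a cause-specific event, and event-free survival is absent from the analysis list in 10.4.3.

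A reader might infer more than the documents support:
- **That the curves are simply biased upward.** This holds only against all-cause PFS or DFS. Against the event as defined, the direction reverses.
- **That a 30% share of unrelated deaths means a 43% longer median (1/(1 − 0.30) − 1).** The 30% is a share of all deaths, not of first PFS events. The progression criteria are broad, so many participants may progress before they die, and the share among first events would then be smaller.
- **That the form codes an unrelated death outside remission as an MDS death.** It has no MDS category; the fault is a gap. If such deaths were in practice entered as progression/relapse, they could count as PFS events, fewer deaths would be censored, and the effect would be smaller than computed.
- **That PFS will be set against published all-cause figures.** No such comparison is planned.
- **That transfusion-dependent participants progress on day 1.** The relapse and progression rows of section 6.3.1 list "transfusion dependence" without a baseline reference, and section 2.1.1 admits lower-risk participants with low hemoglobin "with signs/symptoms of symptomatic anemia or transfusion-dependency". But section 6.3 speaks of worsening cytopenias, and unchanged dependence is not worsening. The passages need reconciling, no more. A day-1 event would in any case shorten PFS, not lengthen it.

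**Conclusion.** The point holds in a limited form. As written, the PFS and DFS curves correspond neither to all-cause progression-free or disease-free survival nor to the probability of escaping the defined event. For PFS, the Kaplan-Meier median exceeds the all-cause median by a factor of about 1.1 to 1.5, with 1.22 (higher risk) and 1.17 (lower risk) in the two worked cases. The same curves lie 8.2 and 5.1 points below one minus cumulative incidence (33.2 − 25.0 and 36.6 − 31.5).

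These sizes rest on constant hazards, on assumed progression hazards, and on applying the protocol's background mortality figures to trial participants. They also assume that unrelated deaths are recognised as such, which Appendix F does not ensure outside remission. That the curves miss both targets does not depend on these particular values, provided some competing deaths are censored. No size can be given for DFS. The definitions leave ORR, OS and LFS untouched, so this should be corrected but does not threaten the trial's main conclusions.

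**What to change.** Define PFS as progression or death from any cause, and DFS as relapse or death from any cause among participants who achieve CR. This follows the plan's own treatment of LFS and makes Kaplan-Meier appropriate. State the censoring rule, for example at the last assessment known to be free of progression or relapse.

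If the cause-specific version is kept, make it a sensitivity analysis: cumulative incidence by Aalen-Johansen with other deaths as competing events. That version also needs a written definition of death from MDS and a primary cause recorded for every death, not only deaths in remission.

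Change sections 1.1.2.2, 3.5.2, 6.3.1, 10.1, 10.4.3 and Appendix D together, so that no old definition remains.

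The cost of the main change is wording only, since date of death, progression and disease status are already collected. The medians will look less favourable, and the definitions will depart from the cited working-group wording, which the report should say.

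Separately, the sponsor should reconcile the transfusion-dependence item in section 6.3.1 with the eligibility text in 2.1.1 and the worsening-cytopenia language in 6.3. Because progression also governs removal from therapy (sections 3.8.1 and 6.3), no wording for that item is proposed here.
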